## Statistical Principles

General principles for analysis include the following:

- The primary analysis will be performed according to the participants' original randomized treatment groups excluding those who do not initiate transfusion of study plasma (modified intention to treat).
- All participants, including those who have withdrawn from the study or were found to be ineligible after randomization, will be included in their assigned treatment group and analyzed for safety.
- All outcomes, including death, following randomization will be included. Death in the absence of known infection will be presumed to be indicative of infection.
- Missing data will be minimized by study design and conduct. It will be addressed analytically using multiple imputation methods

Analyses will be done to explore differences in the outcomes between the treatment groups. Results of these analyses will be presented unadjusted (crude) and adjusted for covariates. Variables chosen for adjustment are specifically for increasing precision in estimates of treatment efficacy and thus must be predictive of disease outcome [Diaz et al, Lifetime Data Anal (2019): 25]. To identify the adjustment variables, we will utilize a hybrid approach of pre-specifying some variables and using an algorithmic approach to identify variables to adjust for among pre-specified candidate variables. Variables that we are near certain to be predictive of outcome will be adjusted for. Age has been consistently related to worse outcomes for COVID-19 and therefore will be included in analyses for adjustment. Other pre-specified variables that will be candidates for inclusion in primary analysis will be determined via an algorithmic approach and these variables will include: clinical site, race, ethnicity, sex, category of exposure, hematology factors and other laboratory markers (i.e., CBC and metabolic panels), body mass index, ABO blood group, prescription steroid, targeted physical exam, and prior comorbidities that have specifically been associated with worse COVID-19 outcomes including: asthma, chronic kidney disease, chronic lung disease (COPD, idiopathic pulmonary fibrosis, cystic fibrosis), diabetes, hemoglobin disorders (thalassemia, sickle cell disease), immunocompromising conditions (cancer, HIV, organ transplantation, prolonged use of corticosteroids), chronic liver disease, hypertension, and serious heart conditions (heart failure, coronary artery disease, cardiomyopathies, pulmonary hypertension), obesity, smoking status, dementia, down syndrome, pregnancy, stroke/cerebrovascular disease, and substance use disorders [updated to CDC list on website on 5/29/2021 and Guan et al Eur Respir J. 2020 May; 55(5)]. To determine which of these pre-specified candidate variables to be included, we will conduct variable selection by random survival forest in the entire sample (i.e., not including an indicator term for treatment arm) and blinded to treatment allocation. The variable importance and 95% confidence intervals [Ishwaran et al Statistics in Medicine. 2019;38] shall be used to identify predictive variables for the outcome and included in analytical models. Specifically, variables in which the 95% CI for the variable importance from the random forest does not contain 0 will be adjusted for. This should reduce the number of variables that the analysis adjusts for in order to minimize the degrees of freedom that are used while allowing the analysis to include the variables that have the most correlation with the outcome in order to maximize precision. This hybrid approach will be done on the full sample (i.e., modified ITT sample) and not include the treatment arm (i.e., among entire sample without controlling for convalescent or control plasma) in order to identify the prognostic baseline variables for entire sample.

The pre-randomization variables listed above (age and the pre-specified candidate variables) will be explored and described according to summary statistics (mean and variance or 25th, 50th, and 75th

percentiles or proportion as appropriate for type of variable) by treatment group and overall. Analyses will be done in the R statistical software.

There will be two formal reviews of interim results. The first will be after 15 infections which is expected to occur near 150 participants reaching day 28 and the second after 50% of the total recruitment has been achieved and these individuals followed to at least day 28. Interim analyses will only be adjusted for age. Stopping guidelines will be based on O'Brien-Flemming boundary. The interim analysis Z-value boundary of 3.03 (nominal p-value of 0.0011, spent alpha 0.0011), 2.38 (0.0087, 0.008), and 1.68 (0.464, 0.408) for a one-sided test with Type 1 of 0.05.

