6. STUDY PROCEDURES

Day -1 to 0

In-person visit

- A. Screening (must be completed before randomization)
- B. Informed consent (may be obtained prior to Day-1 and before performing study related activities)
- C. Baseline Evaluation (at screening)
 1. Demographics (Age, sex ethnicity, race, number of people in household)
 2. Medical history (timing of exposure to COVID-19 source patient, acute and chronic medical condition, medications, allergies. Any medical condition arising after consent should be recorded as AE)
 3. COVID-19 symptom screen (fevers, cough, shortness of breath)
 4. Vital signs
 6. COVID-19 molecular testing prior to infusion, from nasopharyngeal, throat samples (may be omitted if test already performed on same day as part of usual care)
 7. Draw and result ABO and Rh if no documented ABO typing within the past year.
 8. CBC, comprehensive metabolic panel
 9. Stored samples for future studies

10. Urine or serum pregnancy test for females of childbearing potential. Results from laboratory tests obtained up to 7 days before randomization may be used for the pregnancy test.
11. Determination of eligibility as per inclusion/exclusion criteria
12. Confirmation of emergency contact information in EMR.

To the extent possible and with goal of minimizing exposure of health care workers and study team members to risk, there will be a pre-visit explanation and consent done using a video platform at sites that permit video platform use.

Day 0

In-person visit

1. Randomization of eligible subject in IWRS
2. Study Plasma Administration: A single unit of plasma will be transfused. Time at start and end of infusion will be recorded and Vital signs will be measured immediately prior to infusion, 10-20 minutes after start of infusion, at completion of infusion and 30-60 minutes after the end of the infusion.
3. COVID-19 symptom screen (fevers, cough, shortness of breath). Done by telephone before they come in for transfusion.
4. Assessment of clinical status (composite outcome of disease severity)
5. New medical conditions, concomitant medication, AE evaluation
6. Physical examination

Day 1, (+/-) 1 day

In-person visit

1. Vital signs
2. COVID-19 symptom screen (fevers, cough, shortness of breath)
3. Assessment of clinical status (clinical event scale of disease severity)
4. New medical conditions, AE evaluation
5. CBC, comprehensive metabolic panel
6. COVID-19 molecular testing from nasopharyngeal, throat samples

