7. RISKS AND BENEFITS

Potential Benefits of treatment

The potential benefits of antiviral treatment with anti-SARS CoV-2 plasma in patients at high risk for developing COVID-19 due to a close contact with another individual with COVID-19 are unknown. However, it is anticipated that treatment will decrease the risk of developing symptomatic disease and decrease the severity of illness should it develop.

Potential benefits of clinical monitoring and virologic testing

Subjects enrolled in the study will undergo close clinical and virologic monitoring that could facilitate earlier diagnosis of development of COVID-19 with associated benefit to the individual, their family and the community at large.

Potential risks

1. Risks of plasma: Fever, chills, rash, headache, serious allergic reactions, TRALI, TACO, transmission of infectious agents
2. Risks of phlebotomy: local discomfort, bruising, hematoma, bleeding, fainting,
3. Total blood draws will not exceed 500 mL
4. Risks of oropharyngeal and throat swab: local discomfort, vomiting

Alternatives

The alternative to participation in this study is routine care and monitoring following close contact with an individual with COVID-19

Safety measures

1. Safety Evaluations will assess for the safety of high titer anti-SARS-CoV-2 plasma and determine if it is higher, lower or the same as SARS-CoV-2 non-immune plasma
2. Clinical evaluations: In-person vital signs and symptom screen on days 0,1,7,14 and remote (phone call) symptom screens on days ,3 and 60
3. Laboratory evaluations

4. Safety laboratory tests (ABO typing, pregnancy testing, CBC and comprehensive metabolic panel) will be performed at the local CLIA-certified clinical laboratory on days -1 to 0, 1, 7 and 14

Event (AE)

Any untoward medical occurrence in a clinical investigation subject who has received a study intervention and that does not necessarily have to have a causal relationship with the study product. An AE can, therefore, be any unfavorable and unintended sign (including an abnormal laboratory finding, for example), symptom, or disease temporally associated with the use of the study product, whether or not considered related to the study product.

Serious Adverse Event (SAE)

An SAE is any adverse event that results in any of the following outcomes:

1. Death;
2. Life-threatening (immediate risk of death);
3. Inpatient hospitalization or prolongation of existing hospitalization;
4. Persistent or significant disability or incapacity;

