7.1. Reporting Interval

All AEs and SAEs will be documented from the first administration of study product All AEs and SAEs will be followed until resolution even if this extends beyond the study-reporting period. Resolution of an adverse event is defined as the return to pre-treatment status or stabilization of the condition with the expectation that it will remain chronic.

Reporting should also occur at any time after completion of the study, if the investigator becomes aware of a SAE that is suspected to be related to study product

Investigator's Assessment of Adverse Events

The determination of seriousness, severity, and causality will be made by an on-site investigator who is qualified (licensed) to diagnose adverse event information, provide a medical evaluation of adverse events, and classify adverse events based upon medical judgment. This includes but is not limited to physicians, physician assistants, and nurse practitioners.

Laboratory abnormalities will be reported as AEs if they are considered clinically significant by the investigator.

Assessment of Seriousness

- I. Event seriousness will be determined according to the protocol definition of an SAE
- II. Assessment of Severity

Event severity will be assigned according to the MedDRA parameters in the EDC, which correspond to the following definitions:

- 1 = Mild: Transient or mild discomfort (<48 hours); no medical intervention/therapy required.)
- 2 = Moderate: Mild to moderate limitation in activity-some assistance may be needed; no or minimal medical intervention/therapy required)
- 3 = Severe: Marked limitation in activity, some assistance usually required; medical intervention/therapy required, hospitalizations possible
- 4 = Life-threatening: Extreme limitation in activity, some assistance usually required; medical intervention/therapy required, hospitalization or hospice care probable
- 5= Death

Assessment of Association

The association assessment categories that will be used for this study are:

- Associated – The event is temporally related to the administration of the study product and no other etiology explains the event.
- Not Associated – The event is temporally independent of the study product and/or the event appears to be explained by another etiology.

The investigator must provide an assessment of association or relationship of AEs to the study product based on:

- Temporal relationship of the event to the administration of study product;

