## **Power and Sample Size**

We hypothesize that outpatient adults with recent exposure to COVID-19 who receive HCIP will have a lower incidence of developing a SARS-CoV-2 infection with COVID-19 when compared with similar adults receiving control plasma. A sample size of 500 individuals with a high risk exposure within 96 hours of enrollment with a 1:1 allocation ratio to each treatment group will have 80% power to detect a 50% reduction in cumulative incidence by 28 days. This is with a one-sided type 1 error of 5% as we are solely interested in superiority. We assumed that the probability of incident COVID-19 cases is between 0.10 and 0.20 in the control population. We explored several different scenarios with an exponential model to identify the lambda parameter and the package 'powerSurvEpi' for the R statistical software was then used to calculate the sample sizes for these scenarios (See Table1). We assumed that the cumulative incidence of symptomatic disease in SARS-CoV-2 exposed individuals randomized to control plasma to be 0.13X by day 28 and 0.065 (50% reduction in risk) by day 28 among those randomized to HCIP. We therefore estimated 488 participants (244 in each arm). It is

---

\*with surge of infections in December 2020 and hospitals becoming more full, these two were put into the clinical events scale as hospitalization equivalents

anticipated that very few of these subjects will be randomized and not start study plasma infusion (and so be excluded from the primary analysis). Furthermore, it is anticipated that there will be low loss to follow-up prior to development of disease or 28 days (and so have missing data for the primary endpoint). Therefore, we have extended the total sample size to 500 participants. For all analyses, we will use a modified intention-to-treat analyses, which excludes randomized subjects who do not initiate an infusion of the study plasma.

Table 1: Total sample size by the incident proportion of COVID-19 among controls and by percent risk reduction

Proportion of Incident COVID-19 cases at day 28 among controls	50% Risk Reduction	75% Risk Reduction
0.10	648	199
0.13	488	150
0.15	415	129
0.20	298	94

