1. A per-protocol analysis that accounts for those who received a transfusion and were not transfused with their specific treatment group (i.e., non-adherence) using inverse probability weights to account for non-adherence.
2. Classifying participants with missing outcome data at either day 14 or day 28 as having developed COVID-19 with date of COVID-19 being drawn from distribution reflecting the corresponding treatment arms;
3. Multiple imputation of the development of COVID-19 for missing outcomes;
4. A complete case analysis;
5. As convalescent plasma is unlikely to have an immediate effect after transfusion, we will exclude any events occurring between transfusion and 3 calendar days afterwards;
6. As symptoms compatible with COVID-19 may be non-specific and increase false positives, we had elected to use molecular test with or without COVID-19 symptoms as our outcome for any infection and positive test with at least 1 symptom compatible with COVID-19 to define symptomatic infection. As a sensitivity analysis we will conduct a series of analyses that iteratively increases the number of symptoms compatible with COVID-19 required to be present to define symptomatic COVID-19 infection (e.g.,  $\geq 2$ ,  $\geq 3$ , ...). Any individuals who have a pre-existing symptom (perhaps due to prior co-morbidity) that maximizes the number of incident symptoms will be considered positive for any of the sensitivity analyses that are above what they can have. .

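### The SAP gives two conflicting safety populations, and both group safety by assigned arm although transfusion with the other arm's plasma is foreseen

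*SAP*

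**What the plan says.** **Population.** SAP, Power and Sample Size: "For all analyses, we will use a modified intention-to-treat analyses, which excludes randomized subjects who do not initiate an infusion of the study plasma". SAP, Statistical Principles, restricts the primary analysis to those who start a transfusion and then gives safety its own, wider rule. That rule covers "All participants, including those who have withdrawn from the study or were found to be ineligible after randomization". Each of these people, according to the same bullet, "will be included in their assigned treatment group and analyzed for safety".

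**Grouping.** The Statistical Principles rule is by assigned arm. The modified intention-to-treat set also keeps the original randomised groups. Protocol 5.2.1 compares the proportions with an SAE and with a grade 3 or higher event between randomised arms, using Fisher's exact test. No safety set by plasma received is defined.

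**Wrong-unit transfusion.** The first sensitivity analysis under the SAP's Primary Analysis addresses "those who received a transfusion and were not transfused with their specific treatment group (i.e., non-adherence"). It concerns the efficacy outcome only.

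**Start of recording.** Protocol 7.1: "All AEs and SAEs will be documented from the first administration of study product". Protocol 7 defines an adverse event as "Any untoward medical occurrence in a clinical investigation subject who has received a study intervention". Against that, the screening list in Protocol 6 says "Any medical condition arising after consent should be recorded as AE", and the Schedule of Events marks adverse event monitoring in the Baseline column, ahead of Transfusion.

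**Endpoints.** The SAP limits its primary safety endpoints to treatment-related events: severe infusion reactions or ARDS, and grade 3 and 4 events. Protocol 5.3 lists the same events without that limit.

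**The concern.** An analyst cannot follow both SAP sections, so the safety denominator is undefined. Whichever section is followed, the grouping is by assignment. A transfusion reaction is a response to the unit given. If a participant assigned to control receives convalescent plasma and reacts, the assigned-arm table counts the reaction against control plasma.

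Single events can carry weight here. Protocol 8.3 says that two deaths in the intervention arm would probably lead the DSMB to consider stopping. Its Table 2, built on 75 participants per arm and 4 symptomatic cases in the active arm, gives a probability of 0.05 for one death in that arm and 0.001 for two. The SAP also directs special attention to ARDS and deaths in the convalescent plasma group. Blurring the two arms moves a safety comparison towards no difference, which is the unfavourable direction when the question is harm.

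**Working it through.** The plan states no figure for safety (no sample size, power, non-infusion rate, wrong-unit rate or event rate), so there is none to reproduce. The efficacy sample size of 488 is not affected.

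**Step 1. Who can have an event while uninfused?**

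- *Infusion reactions and treatment-related events:* nobody. If Statistical Principles governs, uninfused people are event-free by construction. If the Power and Sample Size rule governs, they are not in the table.
- *All-cause SAEs, all-cause grade 3 and 4 events, and ARDS as Protocol 5.3 lists it:* this depends on the start of recording. Under Protocol 7.1 and the definition in Section 7, uninfused people contribute no events. Under Section 6 and the Schedule of Events, they can.

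**Step 2. Effect on the comparison.** Let pH and pC be the risks with convalescent and control plasma among those infused. Let d be the share of each arm never infused and counted as event-free, and m the share of the infused who receive the other arm's plasma, both equal across arms. The assigned-arm risks are

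- rH = (1 − d)[(1 − m)pH + m·pC]
- rC = (1 − d)[(1 − m)pC + m·pH]

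Hence rH − rC = (1 − d)(1 − 2m)(pH − pC). In the ratio rH/rC the factor (1 − d) cancels, so only m changes it.

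**Step 3. Numbers.** From the plan: 500 participants randomised 1:1, so 250 per arm. Assumed for illustration, because the documents give no values: pH = 10%, pC = 4%, and a range for d and m. By plasma received, the difference is 6.0 points and the ratio 2.50.

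| d | m | rH | rC | Difference (points) | Ratio |
|---|---|---|---|---|---|
| 2% | 0 | 9.80% | 3.92% | 5.88 | 2.50 |
| 10% | 0 | 9.00% | 3.60% | 5.40 | 2.50 |
| 0 | 2% | 9.88% | 4.12% | 5.76 | 2.40 |
| 0 | 5% | 9.70% | 4.30% | 5.40 | 2.26 |
| 2% | 2% | 9.68% | 4.04% | 5.64 | 2.40 |
| 5% | 5% | 9.215% | 4.085% | 5.13 | 2.26 |

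The rows with d = 0 are also what the Power and Sample Size rule gives, because it drops the uninfused: the wrong-unit problem remains. The shrinkage factor is 0.98 × 0.96 = 0.94 at d = m = 2%, and 0.95 × 0.90 = 0.855 at d = m = 5%.

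**Step 4. Power of Fisher's test** (exact, two-sided 0.05, the level being an assumption). At d = m = 2% it is 66% by assigned arm (250 per arm) against 70% by plasma received (245 per group). At d = m = 5% it is 58% against 69% (238 per group).

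**Step 5. How plausible are these values?** With 250 per arm, d = 2% is 5 people per arm uninfused, and m = 2% of the remaining 245 is again about 5 wrong units per arm. At 5% each, the figures are about 12 and 12. One misplaced event changes an arm's rate by 1/250 = 0.4 points and the difference by 0.8.

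**Step 6. Unequal non-infusion.** If d differs between arms, the ratio is multiplied by (1 − dH)/(1 − dC). With 2% and 5% that is 0.98/0.95 = 1.03, still small.

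**The case against.** A reader might infer that adverse events are recorded only after infusion, so that uninfused people count as event-free throughout the safety tables. The documents do not support that. Protocol 6 records conditions arising after consent, the Schedule of Events starts monitoring at baseline, Statistical Principles includes all outcomes after randomisation, and the SAP's missing-data section continues follow-up regardless of compliance. The inference is secure only for infusion reactions and treatment-related events, and only if the Statistical Principles rule governs.

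It can also be said that the safety bullet is the specific rule and should override a general sentence in the sample size section. That is a reasonable reading, but the general sentence explicitly covers all analyses, so the text still needs correcting.

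On wrong units, the only basis is one phrase in an efficacy sensitivity analysis. No mix-up rate is given, and unmasked blood bank staff select each unit from the assignment. Nor do safety decisions rest on the assigned-arm table alone: several halting criteria in Protocol 8.3 act on single events whatever the arm, and one sentence there has the DSMB unmasked for safety reviews (others call it masked). All this bears on size, and it stands. It does not change where a wrong-unit reaction would be counted, since every stated grouping rule is by assignment.

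Finally, an analysis by plasma received gives up strict randomised grouping. That is a real cost, though slight in safety analyses that the SAP itself calls descriptive.

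**Conclusion.** The point holds as a cheap improvement with a small expected effect. The SAP's two population rules conflict. Grouping by assigned arm applies under both and would misplace a wrong-unit reaction. The denominator problem is conditional: it needs the Statistical Principles rule to govern and, for all-cause events and ARDS, recording to start at first administration.

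Equal non-infusion lowers both rates without altering their ratio, and the documents expect very few people to go uninfused. Wrong-unit transfusion distorts the ratio, towards no difference. At 2% for both, the difference shrinks by about 6%. The 14.5% shrinkage at 5% for both needs rates that nothing in the documents supports. A reader might conclude that the planned safety comparison is seriously biased; these figures do not show that.

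The sizes rest on assumed risks and on equal d and m across arms. The conclusion also assumes that no as-received safety set is defined in text that was not available, namely between Protocol 7.1 and 8.2 and before the SAP's Introduction.

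**What to change.** 1. Reconcile SAP Power and Sample Size with SAP Statistical Principles, so that one safety population is stated.
2. Reconcile Protocol 7.1 and the adverse event definition in Section 7 with Section 6 and the Schedule of Events on when recording starts.
3. Define the safety set as all participants who start an infusion, grouped by plasma actually received, and use it for the primary safety endpoints and the Fisher comparisons in Protocol 5.2.1.
4. List separately the events between randomisation and infusion and those in participants never infused, so that the inclusive intent of Statistical Principles is kept.
5. Keep the assigned-arm table as a supportive analysis.

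The cost is a few sentences. No new data collection is needed, and the efficacy analysis and sample size are unchanged. The downside is a slight departure from randomised grouping in the main safety table, which the supportive table covers.
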